### **12.8.1 Additional Participant Randomization Following Withdrawn Participant or Participants Who Discontinue Study Treatment**

Any participant who does not complete the study or misses a dose or requires dose reduction through the post-treatment visit (section 6.2.5) may be replaced by an additional randomized participant. However, all randomized participants will be strongly encouraged to complete all study follow-up, and all randomized participants will be included in the data set for analysis even if their follow-up assessments are incomplete.

## **12.9 Safety Oversight**

### **12.9.1 Safety Review and Communications Plan**

A safety review and communications plan (SRCP) has been developed for the protocol. The SRCP is an internal communications document between the PI and the CSO, which delineates the safety oversight responsibilities of the PI, the CSO, and other stakeholders. The SRCP also includes the overall plan for conducting periodic safety surveillance assessments.

### **12.9.2 Sponsor Medical Monitor**

A medical monitor, representing the IND sponsor (OCRPRO), has been appointed for oversight of safety in this clinical study. The sponsor medical monitor will be responsible for performing safety assessments as outlined in the SRCP.

### **12.9.3 Data and Safety Monitoring Board**

The NIAID intramural DSMB includes independent experts that do not have direct involvement in the conduct of the study and have no significant conflicts of interests as defined by NIAID policy. The DSMB will review the study prior to initiation and twice a year thereafter, and may convene additional reviews as necessary. The board will review the study data to evaluate the safety, efficacy, study progress, and conduct of the study. These reports will be confidential to the DSMB, with data partially unblinded (ie, by treatment group with dummy labels). All SAEs, all Ups, and all IND Safety Reports will be reported by the PI to the DSMB at the same time they are submitted to the IND sponsor. The PI will notify the DSMB of any cases of intentional or unintentional unblinding in writing within 1 business day after site awareness and as soon as possible via email to the DSMB mailbox ([contact]) outlining the reason for the unblinding and the date it occurred. The PI will notify the board at the time pausing or

halting criteria are met and obtain a recommendation concerning continuation, modification, or termination of the study.

### **13 Reporting Procedures**

#### **13.1 Reporting to the NIH IM IRB**

UPs, non-compliance, and other reportable events will be reported to the NIH IM IRB according to NIH HRPP Policy 801.

#### **13.2 Reporting to the NIAID Clinical Director**

The principal investigator will report UPs, major protocol deviations, and deaths to the NIAID clinical director according to institutional timelines.

### **14 Site Monitoring Plan**

According to the International Council on Harmonisation (ICH) E6(R2) Good Clinical Practice (GCP) guidelines section 5.18, and 21 CFR 312.50, clinical protocols are required to be adequately monitored by the study sponsor. This study monitoring will be conducted according to the “NIAID Intramural Clinical Monitoring Guidelines.” Monitors under contract to the NIAID/OCRPRO will visit the clinical research site to monitor aspects of the study in accordance with the appropriate regulations and the approved protocol. The objectives of a monitoring visit will be: 1) to verify the existence of signed informed consent documents and documentation of the consent process for each monitored participant; 2) to verify the prompt and accurate recording of all monitored data points in CRIMSON and prompt reporting of all SAEs; 3) to compare abstracted information entered into CRIMSON with individual participants’ records and source documents (participants’ charts, laboratory analyses and test results, physicians’ progress notes, nurses’ notes, and any other relevant original participant information); and 4) to help ensure investigators are in compliance with the protocol. The monitors also will inspect the clinical site regulatory files to ensure that regulatory requirements (Office for Human Research Protections [OHRP], FDA) and applicable guidelines (ICH GCP) are being followed. During the monitoring visits, the investigator (and/or designee) and other study personnel will be available to discuss the study progress and monitoring visit.

The investigator (and/or designee) will make study documents (eg, consent forms, CRIMSON data abstracts) and pertinent hospital or clinical records, including CRIMSON, readily available for inspection by the local IRB, FDA, the site monitors, and the NIAID staff for confirmation of the study data.

A specific protocol monitoring plan will be discussed with the PI and study staff prior to enrollment. The plan will outline the frequency of monitoring visits based on such factors as study enrollment, data collection status, and regulatory obligations.

## 15 Statistical Considerations

### 15.1 Study Hypotheses

The primary hypothesis is that the MC-QoL at 16 weeks will be different in the sarilumab-treated participants than in the placebo participants. This is a two-sided alpha = 0.05 test and will be covariate-adjusted by the baseline MC-QoL score.

### 15.2 Sample Size Justification

The sample size of 15 per arm is limited by the number of patients available to study. In this section, statistical power is evaluated for a possible treatment effect. The distribution of the total MC-QoL measurement was informed by Siebenhaar et al. Since the data are not normally distributed and the scale is constrained between 0 and 100, a beta distribution with parameters 1.30, 2.41 (multiplied by 100), to match the mean and standard deviation of 35 and 22 as seen in Table 7 of Siebenhaar was used to simulate power. This distribution appears quite consistent with the box plot shown in Figure 1 of Siebenhaar. The Siebenhaar paper also reports a high intraclass correlation of 0.9 for measurements 2 weeks apart, suggesting a strong correlation between the baseline and 16-week scores is plausible; thus, a correlation of 0.7 was assumed in the simulation. While the treatment effect is unknown, power was determined under the assumption that the percentage decline in MC-QoL in the sarilumab-treated arm would be 60% and 10% in the placebo arm (some improvement was anticipated in the placebo arm because these individuals know they might be getting an active treatment). As noted previously, this difference between the arms on MC-QoL is considered clinically meaningful.

The simulation of the trial data was performed as follows. The first step was to generate bivariate standard normal variables with correlation of 0.7. Then the cumulative distribution function of each of these was applied to an inverse cumulative distribution function of a beta with parameters 1.30 and 2.41, yielding pairs of Beta (1.30, 2.41) variables with approximate correlation of 0.7. For example, if a pair of bivariate standard normal generated is 0.880 and 0.642, then these values are transformed to 0.563 and 0.497, respectively, as the probability that a Beta (1.30, 2.41) variable is less than 0.563 equals  $\Phi(0.880)$ , and 0.497 is determined likewise. All beta variables were multiplied by 100 to match the MC-QoL scale. The first member of the pair represented the baseline MC-QoL, and since the protocol excludes MC-QoL under 25, pairs with baseline < 25 were then excluded from all simulated trials. Within each replication, 15 eligible pairs were assigned to the active drug arm, and 15 to the placebo arm. The second member of each pair was multiplied by (1 – the assumed decline for their respective treatment group), representing the 16-week MC-QoL value. Finally, to reflect the integer scores of the scale, all baseline and 16-week values were rounded to the closest integer.

Under the above assumptions, the simulation indicated that a baseline covariate adjusted regression analysis of 16-week MC-QoL value has more than 90% power to show that the

sarilumab-treated arm has superior MC-QoL to the placebo arm. It is noted that this power estimate could be too optimistic, as it is based on limited knowledge of and speculation about the distribution of MC-QoL scores, the correlation between baseline and 16 weeks, and the specific nature of the treatment benefit.

Randomization will continue until there are 30 participants who initiate study drug and have at least the first post-baseline QoL measurement at 4 weeks. Note that participants who do not meet these criteria still remain in the study, and attempts to obtain subsequent QoL measures should be made.

### **15.3 Description of the Analyses**

- Safety analysis: descriptive tabulations of AEs will be constructed. These tabulations will also be stratified by severity.
- Efficacy analysis: the primary analysis of the primary efficacy endpoint will compare treatment groups with a regression analysis, adjusted for baseline QoL. A number of sensitivity analyses are planned for the primary analysis if there are participants with missing data at 16 weeks. Baseline adjusted regression analysis and Wilcoxon rank sum tests will also be applied to a range of efficacy endpoints. Descriptive summaries and graphics will also be provided.

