#### Figure 1 Study Schedule

## 3.2 Study Endpoints

### 3.2.1 Primary Endpoints

1. QoL at 16 weeks post-initiation of study drug/placebo using the MC-QoL.
2. Frequency and severity of AEs during the randomized double-blinded placebo-controlled treatment period.

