## 7 Study Procedures/Evaluations

**Blood draw:** Blood will be collected for clinical safety evaluations (CBC/diff; acute care, hepatic, and mineral panels; total protein; PT/PTT; lipids; serum tryptase; and CRP), storage, collection of DNA and RNA, and to examine serum IL-6 levels and markers of bone marrow resorption and deposition. Blood will also be used to test for HIV, hepatitis B, hepatitis C, and tuberculosis, to determine if the participant's blood cells carry the D816V mutation in the *KIT* gene, which is characteristic of adult ISM and for markers of ISM using flow cytometry. The amount of blood drawn for research purposes will be within the limits allowed for adult research participants by the NIH CC (Medical Administrative Policy 95-9, Guidelines for Limits of Blood Drawn for Research Purposes in the Clinical Center: <http://cc-internal.cc.nih.gov/policies/PDF/M95-9.pdf>).

**Bone marrow biopsy/aspirate:** Bone marrow specimens will be evaluated to determine if the participant's bone marrow carries the D816V mutation in the *KIT* gene and for evaluation of the extent of mast cell infiltration, markers, and morphology.

**Abdominal ultrasound:** Ultrasound of the participant's abdominal area will be conducted to evaluate enlargement of the liver and spleen.

**MC-QoL assessment:** The MC-QoL is a validated health-related QoL survey for adult patients with mastocytosis that consists of 27 items and is divided into four domains: symptoms, social life/functioning, emotions, and skin. The overall disease impairment on QoL is measured by assessing both the total score and the scores of each domain. The MC-QoL is provided in [Appendix C](#).

**SCORMA assessment:** SCORMA evaluates three measures of mastocytosis in a semi-quantitative fashion: extent of skin involvement, lesion activity, and subjective symptoms. The SCORMA chart is provided in [Appendix D](#).

**MSAS assessment:** The MSAS is used to evaluate a patient's experience with 32 symptoms over the course of the previous week. Symptoms are evaluated by severity and distress for eight of the symptoms, and also for frequency for the remaining 24. The MSAS is provided in [Appendix E](#).

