### Laboratory Abnormalities

Decreased neutrophil count less than 1000/ $\mu$ L occurred in patients on combination therapy and occurred in 6% and 4% of patients in the 200-mg sarilumab + DMARD and 150-mg sarilumab + DMARD groups, respectively, compared to no patients in the placebo + DMARD groups. Decrease in ANC was not associated with the occurrence of infections, including serious infections. Decreases in platelet counts less than 100,000/ $\mu$ L occurred in 1% and 0.7% of patients on 200- and 150-mg sarilumab + DMARD, respectively, compared to no patients on placebo + DMARD, without associated bleeding events. Liver enzyme elevations in the pre-rescue placebo-controlled population (sarilumab + DMARD or placebo + DMARD) are summarized in [Table 2](#).

Liver elevation was not associated with clinically relevant increases in direct bilirubin or clinical evidence of hepatitis or hepatic impairment.

Lipid abnormalities (low-density lipoproteins, high-density lipoproteins, and triglycerides) were observed at 4 weeks after initiation of therapy with no additional increases observed thereafter.

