**Table 2: Incidence of Liver Enzyme Elevations in Adults with Moderately to Severely Active Rheumatoid Arthritis**

	Placebo + DMARD N = 579	Sarilumab 150 mg + DMARD N = 579	Sarilumab 200 mg + DMARD N = 582
AST			
> 1× ULN to 3× ULN	15%	27%	30%
> 3× ULN to 5× ULN	0%	1%	1%
> 5× ULN	0%	0.7%	0.2%
ALT			
> 1× ULN to 3× ULN	25%	38%	43%
> 3× ULN to 5× ULN	1%	4%	3%
> 5× ULN	0%	1%	0.7%

Phase 3 placebo-controlled safety population through the pre-rescue period. ALT = alanine transaminase; AST = aspartate transaminase; DMARD = disease-modifying antirheumatic drug; ULN = upper limit of normal.

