## 12.2 Documenting, Recording, and Reporting Adverse Events

All AEs occurring from the baseline visit through the final study visit will be documented, recorded, and reported.

At each contact with the participant, information regarding AEs will be elicited by appropriate questioning and examinations and will be:

- immediately documented in the participant's medical record/source document,
- recorded in CRIMSON, and
- reported as outlined below (eg, IND sponsor, IRB, and FDA).

If a diagnosis is clinically evident (or subsequently determined), the diagnosis rather than the individual signs and symptoms or lab abnormalities will be recorded as the AE.

A laboratory abnormality will not be reported as an AE if ALL of the following criteria are met:

- It is no more than "Grade 1" or "Mild" per the protocol-specified toxicity table (or investigator assessment if not listed on the table); AND
- It does NOT require an intervention (eg, discontinuation of treatment, dose reduction/delay, additional assessments, or treatment); AND
- It is assessed by the PI as NOT related to the study agent(s); AND
- It is assessed by the PI as NOT clinically significant (eg, the abnormal value does NOT suggest a disease or organ toxicity).

All abnormal laboratory findings will be reviewed on a routine basis by the PI to identify potential safety signals. An abnormal lab not included on the toxicity table should be assessed in a similar fashion to the criteria above.

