While the goal is to assess all participants at 16 weeks, regardless of whether they continue with study drug, it is possible that some participants will have missing MC-QoL at 16 weeks. The planned primary analysis, using last observation carried forward, implicitly assumes that study participants who stop getting QoL assessments will be in a stable state, such that the last observed measurement is a reasonable imputation for the 16 week visit. However, to assess the robustness of these results, several sensitivity analysis will be conducted, that implicitly make different assumptions. We will conduct a mixed effects model analysis incorporating all available MC-QoL measurements (this will test the treatment effect at week 16; specifically it will analyze the post-baseline visit timepoints as categorical, and will adjust for the baseline QoL as a covariate.). Another approach imputes participants with missing data at 16 weeks as having the worst scores with a Wilcoxon rank sum test on percent improvement, will be conducted in the mITT population. If there is more than 15% missing data on the 16-week MC-QoL in the mITT population, inverse probability weighting approaches to the linear regression analysis will be done as well in the mITT and ITT populations. Additionally, if the results remain unclear due to missing data, pattern mixture analyses allowing for worse than expected outcomes in those with missing data may be explored.

Other sensitivity analyses will be conducted regardless of whether there are missing data at 16 weeks. We will repeat the primary analysis in the PP population, the mITT2 and mITT3 populations. We will repeat the regression analysis but with a log transformation to both QoL values. To be robust from non-normality, a Wilcoxon rank sum test will also be used to compare the 16-week QoL values in the various analysis populations. Finally, graphical representation of each participant's MC-QoL trajectories over time, color coded by treatment assignment will be constructed.

Baseline adjusted linear regression and Wilcoxon rank sum test will also be used for the secondary and exploratory endpoints. If critical to interpretation, some sensitivity analyses may be conducted.

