A 95% confidence interval of the difference in median percentage improvement will be calculated using a bootstrap. Similarly, standard normal 95% confidence intervals for difference in mean 16-week values, and difference in the mean change from baseline values will be presented. Graphical presentations of baseline and 16 weeks values changes will be completed.

Exploratory analyses might consider analyses with additional covariates and results within subgroups.

Analyses of AEs will be descriptive by study arm, and will also consider severity of AEs.

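### No by-arm summary of the safety laboratory values is planned, so low-grade liver-enzyme, blood-count and lipid changes reach the reported safety results only through blinded case-by-case AE judgement

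*Combined protocol and SAP*

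**What the plan says.** The primary safety endpoint in section 3.2.1 is "Frequency and severity of AEs during the randomized double-blinded placebo-controlled treatment period". Section 15.3 states the safety analysis as "descriptive tabulations of AEs will be constructed. These tabulations will also be stratified by severity". Section 15.5 closes with "Analyses of AEs will be descriptive by study arm, and will also consider severity of AEs". Neither section names a laboratory parameter. The other analyses do not reach them either: "Baseline adjusted linear regression and Wilcoxon rank sum test will also be used for the secondary and exploratory endpoints", and none of the endpoints in sections 3.2.2 and 3.2.3 is ANC, platelets, ALT/AST or lipids.

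The values themselves are collected. Section 7 says "Blood will be collected for clinical safety evaluations" and lists the blood count, hepatic panel and lipids among them. Appendix A places these at baseline and at weeks 4, 8, 12, 16 and 28.

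Section 12.2 governs which laboratory findings become AEs: "A laboratory abnormality will not be reported as an AE if ALL of the following criteria are met". The four criteria are: no more than Grade 1, no intervention needed, judged by the PI not related to study agent, and judged by the PI not clinically significant.

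**The concern.** The laboratory effects in section 8.1 are among the best-described harms of this drug. Neutropenia was the most common reaction leading to discontinuation. Liver enzymes have their own table, "Incidence of Liver Enzyme Elevations in Adults with Moderately to Severely Active Rheumatoid Arthritis". For lipids the section reports: "Lipid abnormalities (low-density lipoproteins, high-density lipoproteins, and triglycerides) were observed at 4 weeks after initiation of therapy".

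The plan holds objective, repeated measurements of all of these in both arms, but the reported safety result uses only the part that becomes an AE. For Grade 1 changes that step is a judgement about one participant at a time, made without knowledge of the arm. A modest shift across one arm shows only when values are pooled by arm, and no such pooling is planned for reporting. Safety is part of the primary objective, so how fully it describes these effects should not depend on how freely mild abnormalities happen to be recorded.

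**Working it through.** **Plan's own figure.** The plan gives no figure for safety. Its one design figure, power above 90% for MC-QoL, reproduces (99.7% in 20,000 simulated trials of section 15.2) but has no bearing on this point.

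**Inputs.** Table 2, placebo and 200 mg:

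| Band | ALT placebo | ALT 200 mg | AST placebo | AST 200 mg |
|---|---|---|---|---|
| >1x to 3x ULN | 25% | 43% | 15% | 30% |
| >3x to 5x ULN | 1% | 3% | 0% | 1% |
| >5x ULN | 0% | 0.7% | 0% | 0.2% |

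There are 15 per arm (section 15.2). Section 12.3.1 cites CTCAE v5.0 without cut-offs, so that Grade 1 for ALT/AST ends at 3x ULN is an assumption.

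**Step 1. Where the excess over placebo lies.** Share = excess in the >1x to 3x band / total excess.
- ALT: 18 + 2 + 0.7 = 20.7 points; 18/20.7 = 87%.
- AST: 15 + 1 + 0.2 = 16.2 points; 15/16.2 = 93%.

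Rounding in the table (zeros taken as exact) gives:
- ALT: from 17/(17 + 3 + 0.75) = 82% to 19/(19 + 1 + 0.65) = 92%.
- AST: from 14/(14 + 1.5 + 0.25) = 89% to 16/(16 + 0.5 + 0.15) = 96%.

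**Step 2. What section 12.2 can remove.** All four criteria must hold. If the investigator calls every mild rise possibly related, nothing is removed. If every mild rise is judged unrelated and not clinically significant, and needs no intervention, the whole band is removed. The unrecorded share of the excess therefore runs from 0% to about 87% (ALT) or 93% (AST). The documents do not allow a narrower range.

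**Step 3. What is certain to be recorded.** Under section 12.6, ALT or AST above 3x ULN, ANC below 1000/µL and platelets below 100,000/µL each trigger a pause. A pause is an intervention, so section 12.2 cannot exclude them. The chance of at least one such liver case among 15 on 200 mg is:
- ALT: 1 - (1 - 0.037)^15 = 43% (expected count 15 x 0.037 = 0.56).
- AST: 1 - (1 - 0.012)^15 = 17% (expected count 15 x 0.012 = 0.18).

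The AE tables could well contain no sarilumab case above 3x ULN. Lipids have no numeric limit in section 12.6 and no rates in section 8.1 by laboratory value, so no corresponding share can be computed.

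**Step 4. What a by-arm table would show.** Expected counts per 15, 200 mg against placebo, in the >1x to 3x band:
- ALT: 15 x 0.43 = 6.5 against 15 x 0.25 = 3.8.
- AST: 15 x 0.30 = 4.5 against 15 x 0.15 = 2.3.

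A Fisher exact test of ALT 43% against 25% at 15 per arm has about 8% power, and the normal approximation gives 17%. For 80% power, 108 per arm would be needed. The summary can describe but not test.

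**The case against.** The strongest reply is that the AE route is better than it looks. Under section 12.3.2, an event is not related only if it has no temporal relationship or is definitely due to another cause, and even an unlikely relation needs poor timing or good evidence of a likelier cause. A new rise after dosing with little evidence of another cause fits the possibly-related category and must be recorded at any grade. This stands: the rule leans towards recording, so the upper ends of the ranges are limits, not predictions.

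Neutropenia also appears to be well captured. Table 1 gives 10% on 200 mg against 0.2% on placebo as a reported reaction, and the chance of at least one among 15 on sarilumab is 1 - 0.90^15 = 79%. That stands too. The arithmetic above concerns liver enzymes and should not be read across to ANC.

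A reader might infer that the values are never compared by arm at all. The documents do not support that. Section 12.9.3 has the DSMB review safety data twice a year by dummy-labelled group. Its laboratory content is unspecified and its reports are confidential, so this does not supply a reported result.

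A reader might also set Table 1 (ALT increased in 5% on 200 mg) against Table 2 (43 + 3 + 0.7 = 46.7% above ULN) and conclude that AE tables catch only 5/46.7 = 11% of elevations. That ratio comes from trials whose AE-recording rules are not in the documents. It marks one low end of an unknown range for this trial.

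Finally, the benefit of laboratory tables is easily oversold. At 46.7% against 26%, sarilumab would show more affected participants than placebo in 84% of trials, but with 26% in both arms this still happens in 42%. The Fisher power is about 11%.

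**Conclusion.** The gap is real. Sections 15.3 and 15.5 plan no reported by-arm summary of ANC, platelets, ALT/AST or lipids, although section 8.1 names these effects and the trial measures them repeatedly. The planned AE analysis matches the stated AE endpoint, so this is an incomplete safety description rather than an inconsistency.

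Its size is uncertain. Between 0% and about 87% of the ALT excess, or 93% of the AST excess, could go unrecorded. This assumes that Grade 1 ends at 3x ULN and that the Table 2 rates carry over to ISM. The second assumption is doubtful in absolute terms: the Table 2 patients were on DMARDs, and section 8.1 says ISM patients generally are not. The gap itself depends on neither assumption.

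The stronger reading, that most of the liver effect will go unreported, is not supported. Exclusion needs all four section 12.2 criteria, and larger changes are caught through the pausing rules.

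**What to change.** Add to sections 15.3 and 15.5 a descriptive by-arm laboratory summary, without hypothesis tests. It should use all measured values, whether or not an AE was recorded:

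- For ANC, platelets, ALT, AST and lipids: observed value and change from baseline at weeks 4, 8, 12, 16 and 28.
- A shift table of baseline category against worst post-baseline category, with the Table 2 bands for ALT and AST. Section 4.2 admits values up to 1.5x ULN, so a shift table is needed to separate existing elevation from change.
- The number and percentage crossing each limit in sections 12.6 and 12.6.3.
- For the open-label period: the same summaries by open-label week and original arm, at the visits where each test is drawn (lipids at weeks 7 and 31 only). Time since first sarilumab dose would not serve, because for the original sarilumab arm it counts the off-drug gap between weeks 14 and 28.

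Before crossings are counted, the ANC units must be reconciled: section 12.6 states the limit per µL and section 12.6.3 per mL.

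The cost is SAP wording and a few tables from data already held. The downside is a longer safety section with small counts that can only be descriptive.
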